## 4.4.1.1.2 Maximum Overall Intensity

Maximum overall intensity is derived from the daily intensities computed as described in Section 4.4.1.1.1 and is calculated as the maximum of the daily intensities over the period considered.

#### 4.4.1.1.3 Presence

Presence is derived from the maximum overall intensity on the period considered:

- None: No presence
- Grade 1, Grade 2, or Grade 3: Presence
- Missing: Missing presence

Subjects with at least one non-missing presence for a specific endpoint will be included in the analysis. Conversely, those without a non-missing presence will not be included in the analysis of the endpoint.

## **4.4.1.1.4** Time of Onset

Time of onset is derived from the daily intensities computed as described in Section 4.4.1.1.1. It corresponds to the first day with intensity of Grade 1, Grade 2, or Grade 3.

Note: If a reaction is not continuous (i.e., reaction occurs over two separate periods of time intervened by at least one daily intensity Missing or None) then the time of onset is the first day of the first occurrence.

Categories for time of onset are as follows

- D0-D3
- D4-D7

#### 4.4.1.1.5 Number of Days of Occurrence

Number of days of occurrence over the period considered is derived from the daily intensities computed as described in Section 4.4.1.1.1. It corresponds to the number of days with daily intensities of Grade 1, Grade 2, or Grade 3. Number of days of occurrence on the solicited period with a specified intensity may also be derived.

Categories for number of days of occurrence during the solicited period are as follows

• 1-3 days

- 4-7 days
- 8 days

#### 4.4.1.1.6 Overall Number of Days of Occurrence

If a reaction is ongoing at the end of the solicited period, then the overall number of days of occurrence is derived from the daily intensities and the stop date of the reaction after the end of the solicited period. The overall number of days of occurrence is:

• (stop date – last vaccination date) + (number of days of occurrence within the solicited period) – length of the solicited period + 1

If the stop date is missing or incomplete (contains missing data [MD]), the overall number of days of occurrence will be considered as Missing.

Categories for overall number of days of occurrence are as follows

- 1-3 days
- 4-7 days
- $\geq 8$  days
- Missing

## 4.4.1.1.7 Ongoing

Ongoing is derived from the last daily intensity of the solicited period computed as described in Section 4.4.1.1.1 and the maximum intensity on the ongoing period. The investigator's ongoing flag is not used because the measurement would determine the ongoing status of the reaction. Note: The intensity could be considered None (not a reaction) in the analysis despite being considered a reaction by the investigator (e.g., fever > 37.5°C but < 38°C). If the last daily intensity of the solicited period is at least Grade 1 and maximum intensity on the ongoing period is also at least Grade 1, then the reaction is considered ongoing. In any other cases the reaction will not be considered as ongoing.

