## 4.4 Derived Endpoints: Calculation Methods

#### **4.4.1** Safety

#### 4.4.1.1 Solicited Reactions

## 4.4.1.1.1 Daily Intensity

All daily records for solicited reactions will be derived into daily intensity according to the following classification: None, Grade 1, Grade 2, Grade 3, or Missing.

For measurable injection site reactions (Erythema/Swelling):

Grade 1: > 0 to < 25 mm

Grade 2:  $\geq$  25 to  $\leq$  50 mm

Grade  $3: \ge 50 \text{ mm}$ 

For measurable systemic reactions (Fever):

Grade 1:  $\geq$  38.0°C to  $\leq$  38.4°C

Grade  $2: \ge 38.5$ °C to  $\le 38.9$ °C

Grade  $3: \ge 39.0$ °C

For the derivation of daily intensities the following sequential steps will be applied:

- 1) Solicited reactions (except Fever/Pyrexia) with an investigator presence recorded as "No" and with all daily records missing then all daily intensities will be derived as None.
- 2) For a temperature partially missing after decimal point, the data will be analyzed replacing "MD" (missing data) by zero. For example, a "39.MD" daily temperature will be considered as "39.0°C" at the time of analysis.

3) For non-measurable solicited reactions, the daily intensities will correspond to the daily records reported in the clinical database. For measurable solicited reactions, the daily measurements reported in the clinical database will be converted based upon the intensity scales defined in the protocol; this assumes that a reaction that is too large to measure (non measurable, "NM") is Grade 3. Note: The maximum intensity on the ongoing period is derived from the record of the maximum intensity/measurement after the end of the solicited period following the rule described above.

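### SAP 4.4.1.1.7 gives a Missing Day 7 or later intensity the same result as a recorded None, so a stop date after D07 goes unused and overall duration is usually understated

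*SAP*

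**What the plan says.** SAP 4.4.1.1.7 sets two conditions. The first is that "the last daily intensity of the solicited period is at least Grade 1". The second is that the "maximum intensity on the ongoing period is also at least Grade 1, then the reaction is considered ongoing". Everything else falls under the default: "In any other cases the reaction will not be considered as ongoing".

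The same section explains why the investigator's view is set aside: "The investigator's ongoing flag is not used because the measurement would determine the ongoing status of the reaction". Its example is a temperature that the investigator regards as fever but that lies below 38°C and so grades as None.

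SAP 4.4.1.1.1 lists the levels of a daily intensity as "None, Grade 1, Grade 2, Grade 3, or Missing", so Missing and None are separate values. The post-period maximum is "derived from the record of the maximum intensity/measurement after the end of the solicited period" under the same grading rule.

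SAP 4.4.1.1.6 combines in-period intensities with the stop date, but only conditionally: "If a reaction is ongoing at the end of the solicited period, then the overall number of days of occurrence is derived". Its Missing category is triggered only by an absent or incomplete stop date, not by an absent intensity. Neither section says what overall number of days a non-ongoing reaction receives.

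**The concern.** The SAP's reason for overriding the flag is sound when a measurement exists and grades as None. It does not reach a blank, where nothing has been measured that could overrule the investigator. It also fits poorly with pain, headache, malaise and myalgia, four of the seven solicited reactions, which carry a parent-reported grade and no measurement.

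Neighbouring rules keep missing data visible or treat them cautiously. Presence (4.4.1.1.3) separates missing from absent, 4.4.1.1.6 shows a missing stop date as its own category, and 5.3.1.2 counts missing causality as related. In 4.4.1.1.7 a blank instead yields the shorter-duration answer with no trace in the table.

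At stake is the description of how long booster reactions last. Under this rule a Missing value can only remove ongoing status, so any error it causes shortens the reported duration. Information that could prevent this is planned: diary recording runs to resolution (Protocol 9.2.3.2), and related events are followed until they resolve, stabilise or become chronic (Protocol 5.1.4).

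**Working it through.** **Inputs.** The two conditions and the default come from SAP 4.4.1.1.7, the formula and categories (1-3, 4-7, ≥ 8 days, Missing) from 4.4.1.1.6, and the in-period count from 4.4.1.1.5, where only days of Grade 1 or more count and a blank adds nothing. The solicited period runs D0 to D07 (SAP 3.2), which is 8 days.

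**Formula.** Let S be the stop day after vaccination, n the graded days within D0 to D07, and L the period length. Overall days = S + n − L + 1.

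**Check of the formula.** For a continuous reaction from D0 to D9: 9 + 8 − 8 + 1 = 10, the correct inclusive count. Over all continuous reactions with onset D0 to D7 and stop D8 to D44, the formula equals the inclusive count when L = 8 and fails when L = 7. So L = 8 is the intended length.

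**Assumption.** For a non-ongoing reaction I count only the graded days in D0 to D07. This is an inference.

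**Worked cases.**

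1. Grade 1 on D4 to D6, Day 7 blank, later maximum Grade 2, stop D12. Condition 1 fails, so the reaction is not ongoing: 3 days, category 1-3. Formula: 12 + 3 − 8 + 1 = 8 days, category ≥ 8.
2. Grade 1 on D6 and D7, later intensity blank, stop D12. Condition 2 fails: 2 days, category 1-3. Formula: 12 + 2 − 8 + 1 = 7 days, category 4-7.
3. Graded D0 to D6, Day 7 blank, graded later, stop D20. Not ongoing: 7 days, category 4-7. Formula: 20 + 7 − 8 + 1 = 20 days, category ≥ 8. The inclusive count is 21; the formula gives one fewer because the blank Day 7 adds nothing.
4. Graded on all of D0 to D07, later intensity blank. The count is 8 days, so the category stays ≥ 8 whatever the stop date.

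**Reach.** Take continuous reactions with onset D0 to D7 (8 values) and stop D8 to D30 (23 values): 8 × 23 = 184 patterns. Compare the category from graded days with the category from the inclusive count.

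- Day 7 Missing: too low in 180, correct in 184 − 180 = 4. Of the 180, 23 are Day 7 onsets with no graded day left in the period.
- Later intensity Missing: too low in 152, correct in 184 − 152 = 32. Of the 32, 23 are the D0 onsets of case 4.

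These counts show which patterns are exposed, not how often they will occur.

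**Search for a rescuing rule.** SAP 5.3.1.4 refers missing solicited intensities back to 4.4.1.1.1. The only whole-record rule there sets intensities to None when presence is recorded as No and every daily record is missing (fever excepted). SAP 5.3.1 says safety data are not replaced. Nothing covers a single blank at Day 7 or afterwards.

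**The case against.** The strongest reply is that this is a disclosed classification rule with little reach. The protocol's endpoint is the number of days of reactions up to 7 days after vaccination (9.2.2), and the table that serves it (SAP 4.4.1.1.5) does not use the ongoing rule. Neither do incidence, time of onset or solicited-period maximum intensity. Grouping Missing with None also has a precedent: 4.4.1.1.4 lets either one break a reaction into separate episodes. All of this stands, and it limits the point to ongoing status and the overall-days table.

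The blanks should also be rare. Parents are telephoned from D08, the diary is reviewed at Visit 2 (Protocol 5.1.4), and gaps are clarified or queried (Protocol 11.1, 11.2, 13.2). A blank Day 7 beside a later grade and a stop date is what these steps should catch. That makes few cases likely but does not supply a rule for those that remain.

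A reader might infer that every affected reaction is misclassified. It is not: 4 and 32 of the 184 patterns keep the right category. Nor do incomplete diaries always shorten durations, since an ongoing reaction without a complete stop date goes to Missing. Nor does the SAP say that a blank proves the reaction stopped; it only withholds ongoing status.

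A reader might also infer that the flag should simply be reinstated. For fever that would bring back the sub-threshold temperatures that 4.4.1.1.7 means to exclude. Finally, if the last daily intensity means the last non-missing one, cases 1 and 3 disappear. The SAP does not say so, and case 2 stands under either reading.

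**Conclusion.** The point holds within these limits. SAP 4.4.1.1.7 does not separate Missing from None, and its stated reason covers only None. Together with 4.4.1.1.6, this leaves a recorded stop date after D07 unused whenever the Day 7 intensity or the later maximum is blank. If non-ongoing reactions are counted by graded solicited days, overall duration is usually understated, by 5 days in case 1 (8 − 3) and 5 in case 2 (7 − 2). The documents give no rate of diary gaps, so the number of children affected cannot be estimated; it is probably small. The study is descriptive and no hypothesis test is involved. The correction is worth making because the error runs one way and the remedy is cheap.

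**What to change.** Amend SAP 4.4.1.1.7 as follows:

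- Apply the not-ongoing default only when the Day 7 intensity or the later maximum is derived as None.
- When one of the two is Missing and the other is at least Grade 1, treat the reaction as ongoing if a complete stop date after D07 is recorded, and apply the 4.4.1.1.6 formula with the period length stated as 8 days.
- Assign the existing Missing overall-days category to fever with one value Missing, because the unrecorded temperature may be sub-threshold. Do the same where no complete stop date is recorded, or where both values are Missing but the flag or a stop date points to continuation.
- List all reactions where the investigator's flag and the derived status disagree.

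In 4.4.1.1.6, add a sentence saying how overall days are counted for a non-ongoing reaction.

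The cost is a few lines of SAP text, a small programming change and one listing. The downside is that a few durations will rest on a stop date rather than a graded entry, or will move to Missing.

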#### 4.4.1.2 Unsolicited Non-serious AEs

#### 4.4.1.2.1 Presence

An observation will be considered an event if it has at least a verbatim term and is not a Grade 0 intensity event. Grade 0 events should be included in the listing "Unsolicited non-serious adverse events not included in the safety analysis."

### **4.4.1.2.2** Intensity

Intensity for unsolicited non-serious AEs will be derived according to the following classification: None, Grade 1, Grade 2, Grade 3, or Missing.

If the unsolicited non-serious AE is measurable and its preferred term (PT) is part of the list of solicited reactions, then the measurement is derived based upon and following the same rule as the intensity scales defined in the protocol for that measurable injection site or systemic reaction. Intensity for the other unsolicited non-serious AEs will correspond to the value reported in the CRF.

The maximum intensity corresponds to the highest intensity for a unique term.

#### 4.4.1.2.3 Last Vaccination

Last vaccination before an unsolicited non-serious AE is derived from the visit numbers provided in the clinical database and is calculated as follows:

- If an unsolicited non-serious AE has a non-missing visit number, the visit number should be used to determine the last vaccination before the unsolicited non-serious AE
- If the visit number is missing, then the start date should be used to determine the last vaccination before the unsolicited non-serious AE

#### **4.4.1.2.4** Time of Onset

Time of onset is derived from the start date of the unsolicited non-serious AE provided in the clinical database and the date of last vaccination:

• start date of the unsolicited non-serious AE – date of previous vaccination

The time of onset should be considered as missing only if one or both of the dates are missing or partially missing.

The unsolicited non-serious AEs will be analyzed "Within 30 days", which corresponds to AEs with a time of onset between D0 and D30 days after vaccination or missing. An AE with missing time of onset will be considered to have occurred just after the vaccination indicated by the visit number, so will be included in these tables.

Note: Unsolicited non-serious AE that occurred before vaccination (negative time of onset) or with a time of onset higher than defined above will not be included in analysis, but will be listed separately.

Time of onset will be displayed as follows:

- D0-D3
- D4-D7
- D8-D14
- $\geq$  D15
- Missing

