5.1 Description of the Overall Study Design and Plan

5.1.1 Study Design

This is a Phase III, open-label, multi-center study to describe the immune persistence of the priming dose and describe the immunogenicity and safety of a booster dose of MenACYW conjugate vaccine in children in Finland who had been vaccinated 3 years earlier as toddlers with either MenACYW conjugate vaccine or Nimenrix® as part of the MET54 study.

Subjects who were vaccinated 3 years (\pm 45 days) earlier at 12 to 23 months of age in study MET54 will be eligible for enrollment in study MET62.

All subjects will receive a single dose of MenACYW conjugate vaccine on Day (D) 0.

All subjects will provide blood samples for immunogenicity assessment at baseline (prevaccination) and at 30 to 44 days after vaccination.

Solicited AE information will be collected for 7 days after vaccination; unsolicited AE information will be collected from Visit 1 (D0) to Visit 2 (D30 [+14 days]), and SAE information (including adverse events of special interest [AESIs]) will be collected throughout the study period.

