5.1.3 Study Plan

A schedule of assessments and study vaccinations is provided in the Table of Study Procedures.

Vaccination

All subjects will receive a single dose of MenACYW conjugate vaccine at Visit 1 (D0).

Blood Sampling

All subjects will provide a pre-vaccination blood sample on D0 and a post-vaccination sample at Visit 2 (30 to 44 days after the vaccination at Visit 1).

Collection of Safety Data

- All subjects will be observed for 30 minutes after vaccination and any unsolicited systemic AEs occurring during that time will be recorded as immediate unsolicited systemic AEs in the electronic case report form (CRF) (see Section 9.2.3.1).
- The subject's parent / legally acceptable representative will record information in a diary card (booklet or electronic device [e-diary]) about solicited reactions from D0 to D07 after vaccination and unsolicited AEs from D0 to Visit 2. SAEs will be reported throughout the duration of the trial.
- In addition, the subject's parent / legally acceptable representative will be asked to notify the site immediately about potential SAEs at any time during the trial.
- Alerts will be sent to the e-diary (if applicable) and staff will contact the subject's parent / legally acceptable representative by telephone on D08 (+2 days) to identify the occurrence of any SAE not yet reported, and to remind them to complete the diary card (booklet or e-diary) up to Visit 2 and to bring it back at Visit 2.
- The completed diary card (booklet or e-diary) will be reviewed with the subject's parent / legally acceptable representative at Visit 2.

Note: The diary card may be either a booklet or an electronic device that contains an application to enter the information (e-diary).

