9.2.2 Safety Endpoints

The endpoints for the evaluation of safety are:

- Occurrence, nature (Medical Dictionary for Regulatory Activities [MedDRA] preferred term [PT]), duration, intensity, and relationship to vaccination of any unsolicited systemic AEs reported in the 30 minutes after vaccination
- Occurrence, time of onset, number of days of occurrence, intensity, action taken, and whether
 the reaction led to early termination from the study, of solicited (prelisted in the subject's
 diary card [booklet or e-diary] and CRB) injection site reactions occurring up to 7 days after
 vaccination.
- Occurrence, time of onset, number of days of occurrence, intensity, action taken, and whether
 the reaction led to early termination from the study, of solicited (prelisted in the subject's
 diary card [booklet or e-diary] and CRB) systemic reactions occurring up to 7 days after
 vaccination.
- Occurrence, nature (MedDRA PT), time of onset, duration, intensity, action taken, relationship to vaccination (for systemic AEs only), and whether the event led to early termination from the study, of unsolicited AEs up to Visit 2 after vaccination.
- Occurrence, nature (MedDRA PT), time of onset, duration, seriousness criteria, relationship to vaccination, outcome, and whether the SAE led to early termination from the study, of SAEs, including AESIs, throughout the trial.

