### **5.3.1.5** Start Date and Stop Date

Missing or partially missing start dates for unsolicited AEs will remain missing and not be imputed. If either the start or stop date is missing or partially missing, the time of onset will be

considered to be missing. Nevertheless unsolicited AEs with missing time of onset will be included in analyses according to the visit collected.

Missing or partially missing stop dates for AEs (solicited reactions and unsolicited AEs) will remain missing and not be imputed.

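### Unsolicited non-serious AEs are tabulated only to D30 although the endpoint runs to Visit 2 (D30 to D44), and two SAP sections disagree on when onset is missing

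*SAP*

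**What the plan says.** **Endpoint and collection.** Protocol 9.2.2 defines the endpoint as "unsolicited AEs up to Visit 2 after vaccination". Protocol 5.1.3 has parents record "solicited reactions from D0 to D07 after vaccination and unsolicited AEs from D0 to Visit 2". Protocol 5.1.1 and SAP 3.1 give the same collection period and put Visit 2 at D30 with a window of +14 days.

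**Analysis window.** SAP 4.4.1.2.4 gives unsolicited non-serious AEs one period, *Within 30 days*, "which corresponds to AEs with a time of onset between D0 and D30 days after vaccination or missing". An AE "with a time of onset higher than defined above will not be included in analysis, but will be listed separately".

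**Shorter wording in the protocol.** Section 5.1.2 describes safety assessment up to 30 days. Section 9.2.3.3 refers to a 30-day period for recording other medical events, but to 30 (+14) days for SAEs. SAP 4.2 refers to the whole of Protocol 9.2 and so takes in both windows.

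**Missing onset.** SAP 4.4.1.2.4 computes onset as the AE start date minus the vaccination date and adds: "The time of onset should be considered as missing only if one or both of the dates are missing or partially missing". SAP 5.3.1.5 has a different condition: "If either the start or stop date is missing or partially missing, the time of onset will be" treated as missing. It goes on to say that unsolicited AEs with missing onset are "included in analyses according to the visit collected".

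**Changes.** SAP 5.7 declares only the added analysis set for persistence and says nothing about the AE window.

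**The concern.** There are two separate defects.

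First, the tables cover a shorter period than the endpoint. For non-serious AEs, the counts, percentages, confidence intervals and breakdowns by SOC/PT, intensity and relatedness would all stop at D30. The *Within 30 days* label makes this visible, but no planned summary covers the full endpoint period. SAEs do get one: SAP 4.4.1.3.2 analyses them both within 30 days and during the study.

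Second, the SAP's two rules for missing onset conflict. Because missing-onset AEs are counted, the choice of rule decides whether some AEs after D30 enter the tables, and it moves some earlier AEs into the *Missing* onset category. Two programmers following the SAP could produce different AE counts and different onset distributions from the same data. Time of onset is itself a named attribute of the endpoint in Protocol 9.2.2.

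**Working it through.** **Step 1. Visit 2 window.** Inputs: D30 and +14 days (Protocol 5.1.1). 30 + 14 = 44, which reproduces the 30 to 44 days of participation stated in the protocol synopsis.

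**Step 2. Follow-up outside the tables.** Days are counted inclusively from D0.
- SAP window D0 to D30: 30 + 1 = 31 days.
- Days collected with Visit 2 on day v: v + 1.
- Days outside the tables: (v + 1) − 31 = v − 30.

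| Visit 2 on | Days collected | Outside the tables | Share |
|---|---|---|---|
| D30 | 31 | 0 | 0% |
| D37 | 38 | 7 | 7/38 = 18.4% |
| D44 | 45 | 14 | 14/45 = 31.1% |

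These are days, not events. The documents give no AE rate, no distribution of Visit 2 dates and no rate of missing stop dates, so the number of AEs affected cannot be derived.

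**Step 3. Both onset rules applied to the same AEs.** The vaccination date is known and Visit 2 is on D44.

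| AE | SAP 4.4.1.2.4 | SAP 5.3.1.5 |
|---|---|---|
| Start D35, stop D40 | Onset D35; listed only | Onset D35; listed only |
| Start D35, no stop date | Onset D35; listed only | Onset missing; counted |
| Start D5, no stop date | Counted in D4-D7 | Counted in *Missing* |
| Start date missing | Onset missing; counted | Onset missing; counted |

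The second row changes the number of AEs counted; the third changes the onset distribution. Comparing the first two rows, under 5.3.1.5 two AEs that start on the same day after D30 are treated differently according to whether a stop date was obtained. The SAP gives no reason for that.

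**Step 4. Are missing stop dates expected?** Yes. The footnote in Protocol 9.2.3.3 says AEs with no stop date obtained during the study are regarded as ongoing at its end.

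**Step 5. What is not lost.**
- SAEs keep a whole-study period (SAP 4.4.1.3.2), and AESIs are collected as SAEs (SAP Table 3.1 footnote).
- Discontinuations recorded on the termination form still count in the disposition and safety overview tables (SAP 4.4.1.4.6).
- The SOC/PT discontinuation table is restricted to the stated period, so there a non-serious AE with known onset after D30 drops out.

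**The case against.** The strongest reply is that the 30-day window comes from the protocol. Section 9.2.3.3, the working section on unsolicited AEs, uses it for recording, and section 5.1.2 uses it for safety assessment overall. On that reading the SAP picked one of two available windows, and SAP 5.7 had no change to declare. A fixed window is also sound in itself: it gives every child seen within the Visit 2 window the same 31 days, whereas percentages to Visit 2 mix unequal follow-up. Later AEs remain visible in a listing.

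On the onset rule, the AE count changes only for a known start after D30 combined with an incomplete stop date. The Protocol 9.2.3.3 footnote also says stop dates of related AEs are actively sought. The formula and the word *only* in SAP 4.4.1.2.4 make the intention fairly clear, so 5.3.1.5 is probably a drafting slip: duration (SAP 4.4.1.2.5) is the quantity that needs both dates.

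Much of this stands, and it limits the weight of the point. The 30-day table deserves to stay, and the protocol shares the blame for the mismatch. But 9.2.2 is the endpoint definition, and it runs to Visit 2. A protocol with two windows is a reason to state which one was used. A probable slip is still a written rule that gives a different result.

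**Conclusion.** Both defects hold. As written, the tables for unsolicited non-serious AEs leave out between 0% and 31% of a child's collected follow-up days, depending on when Visit 2 takes place. This assumes attendance within D30 to D44. Independently of the window, SAP 5.3.1.5 contradicts SAP 4.4.1.2.4 on missing onset and can change both counts and onset categories.

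The impact is minor to moderate. The study is descriptive, no test or sample size depends on this, SAEs are tabulated for the whole study, and the late AEs are listed. It should still be corrected before analysis, because safety tables are a main output of a study of this kind and the correction is small.

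**What to change.** 1. **SAP 5.3.1.5:** remove the stop date from the onset rule, so that onset is missing only if the start date or the vaccination date is missing or partial, as in 4.4.1.2.4. This is a wording change only.
2. **SAP 4.4.1.2.4:** add a D0-to-Visit 2 summary of unsolicited non-serious AEs for the 9.2.2 endpoint, mirroring the SAE periods in 4.4.1.3.2. Keep *Within 30 days* beside it as the uniform-window summary.
3. **SAP 5.7:** record any D30 restriction that is kept, with the reason.
4. **Protocol 5.1.2, 9.2.2 and 9.2.3.3:** reconcile to one stated window. Changing the protocol text would need an amendment under Protocol 5.4. Parts of the SAP already describe conduct in the past tense, so if an amendment is no longer practical, a note in SAP 5.7 can record the reconciliation.

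The SAP cost is some wording and one extra set of AE tables on data already collected. The last dated onset category (D15 or later) already holds D31 to D44, so no new category is needed. Follow-up in the added tables will differ by up to 14 days between children seen in window, which should be footnoted.
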